9.2.1.5.7. King's ALS Clinical Stage Derived from ALSFRS-R Score and Death Event

All analyses will be done using the FAS. A shift table to each visit up to week 48 from each baseline category will be summarized using number and percentages.

For the Kings ALS Clinical Staging System, attention will focus on two events of clinical

progression:

- Any decline in stage from baseline
- Any ≥ 2 -stage decline from baseline

These events will be analyzed in terms of both the proportion of patients who will experience the events between baseline and week 48 using chi square test for proportions, as well as the time to these events using stratified Log-rank test. For the latter, study dropouts prior to any event will be treated as censored as of the date of their first missing assessment. The time to event will be also displayed using the Kaplan Meier figure. Comparisons will be made between treatment groups on an overall basis, as well as controlling for stage at baseline.

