4. STUDY DESIGN

4.1. Study Design

This is a Phase 3b, multicenter, double-blind, parallel group, randomized, study that will evaluate the efficacy and safety of 2 treatment regimens of edaravone for a period of 48 weeks in subjects with ALS as follows:

- Group 1: Edaravone 105 mg oral dose once daily for 48 weeks
- Group 2: Edaravone 105 mg oral dose in for 14 days, followed by a 14-day placebo. Subsequently, repeat edaravone 105 mg oral dose in for 10 days followed by 18-day placebo (regimen denoted as on/off).

Eligible subjects will be randomized at baseline in a 1:1 ratio to receive 1 of 2 treatment groups. Randomization will be stratified according to ALSFRS-R rate of decline score for 8 weeks screening period (2 levels strata of -1,-2 or -3,-4) and geographical region (3 levels strata of Europe, America or Asia Pacific).

Concomitant use of riluzole is permitted when the doses and regimens will remain unchanged from the day of evaluation of ALSFRS-R at the screening visit, through the end-of-treatment (EOT) or early termination (ET). Although dose reduction, dose interruption or discontinuation due to the onset of AEs, progression of dysphagia, or gastrostomy while on oral edaravone 105 mg are allowed, it is prohibited to initiate the use of riluzole. Subjects who initiate riluzole therapy de-novo during the treatment period will be discontinued from the study. The use of AMX0035 will be allowed for patients in the event that it becomes commercially available via prescription in their respective country. AMX0035 should be taken at least 1 hour after MT-1186.

This study consists of a screening period of 8 weeks, a double blind treatment period of 48 weeks, and a safety follow-up period of 2 weeks. A schedule of assessment of all study procedures is provided in Table 1.

- **Screening period:** Screening assessments will be performed up to 8 weeks (\pm 7 days) prior to Day 1. All screening evaluations must be completed and reviewed to confirm that potential subjects meet all eligibility criteria. If a subject has not met all eligibility criteria at the end of the screening period, the subject will be registered as a screen fail. Screen fail subjects may be eligible for re-screening 1 time.
- **Double-blind Treatment Period:** Subjects who successfully complete the screening period will return to the study clinic on Day 1 in a fasting state (eg, without breakfast) and inclusion

Statistical Analysis Plan
Protocol No. MT-1186-A02

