7.2. Statistical Tests

Unless otherwise specified, all statistical tests will be done as 2-sided at the 5% significance level. Point estimates of treatment differences will be accompanied with 2-sided 95% confidence intervals (CIs) where applicable.

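### King's-stage progression proportions are compared with a chi-square test that ignores the randomisation strata: valid, but it may lose some power if decline rate is prognostic

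*SAP*

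**What the plan says.** SAP 9.2.1.5.7 defines two progression events on the King's staging: "Any decline in stage from baseline", and a decline of two or more stages. For each event the SAP compares "the proportion of patients who will experience the events between baseline and week 48 using chi square test for proportions". A second analysis is named in the same sentence: "as well as the time to these events using stratified Log-rank test". No stratification factor is attached to the chi-square, and the strata of the log-rank test are not listed there. The section closes with: "Comparisons will be made between treatment groups on an overall basis, as well as controlling for stage at baseline". It names no method for that adjusted comparison.

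On allocation, SAP 4.1 says "Eligible subjects will be randomized at baseline in a 1:1 ratio to receive 1 of 2 treatment groups". It continues: "Randomization will be stratified according to ALSFRS-R rate of decline score for 8 weeks screening period (2 levels strata of -1,-2 or -3,-4"). The second factor is "geographical region (3 levels strata of Europe, America or Asia Pacific"). That makes 2 × 3 = 6 strata.

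Elsewhere the SAP adjusts for both factors. The %SVC model in 9.2.1.4.1 includes them, the ALSAQ40, ALSFRS-R, %FVC and body-weight models reuse that specification, and the Cox model in 9.2.1.4.3 includes them too. SAP 7.2 sets the general rule that "all statistical tests will be done as 2-sided at the 5% significance level".

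**The concern.** Stratified 1:1 allocation balances the arms within each stratum. Chance imbalance in the strata therefore no longer adds to the variance of the difference in proportions. Pearson's chi-square does not know this: it uses the pooled variance, which still contains the between-stratum part. If a stratum predicts the event, the standard error is too large, the true size falls below 5%, and power is lost.

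The link is plausible here. SAP 8.4.2.8 derives King's stage from ALSFRS-R items and death, and one randomisation factor is the recent decline on that same scale. At stake is some sensitivity in one secondary comparison. The proportion test is also a visible exception to the SAP's own habit of adjusting for both factors, and no reason is given.

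**Working it through.** **Plan's own figure.** The documents state no power or event rate for the King's tests. The nearest stated figure is the 85.5% power for ALSFRS-R (SAP 4.2). With 190 × 0.7 = 133 completers per arm, the noncentrality is 2.6 / (7 × √(2/133)) = 3.03 on 264 degrees of freedom. A two-sided 5% t-test then has 85.50% power, so the figure reproduces. It does not bear on the King's comparison, which needs assumed rates.

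**Inputs.** From the documents: 380 subjects, 1:1 allocation, 2 × 3 strata, two-sided 5%. Assumed: event rates in slow (-1, -2) and fast (-3, -4) decliners, the split between them, no region effect on the event, and all 380 analysed.

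**Size by formula.** Let r² = Σ w·p(1−p) / [p̄(1−p̄)], the mean within-stratum variance over the pooled variance. The size of the unstratified test is about 2·[1 − Φ(1.96/r)].

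Example: rates 50% and 80%, equal split. Within-stratum variance is 0.5 × 0.25 + 0.5 × 0.16 = 0.205. Pooled variance is 0.65 × 0.35 = 0.2275. So r = √(0.205/0.2275) = 0.949, and the size is 2·[1 − Φ(1.96/0.949)] = 3.9%.

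With an equal split, the formula gives 5.0% at 60/60, 4.9% at 65/75, 4.5% at 60/80, 3.9% at 50/80 and 3.2% at 40/80.

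**Simulation, set A.** Permuted blocks of 4 within six strata (block size assumed), 40,000 trials under no effect and 20,000 at odds ratio 0.55. CMH is stratified by decline rate.

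| Slow / fast rate | Split | Size: chi-square | Size: CMH | Power: chi-square | Power: CMH |
|---|---|---|---|---|---|
| 60 / 60 | 50:50 | 5.3% | 5.3% | 82.0% | 81.9% |
| 65 / 75 | 50:50 | 5.0% | 5.1% | 78.9% | 79.1% |
| 60 / 80 | 50:50 | 4.7% | 5.2% | 76.0% | 77.6% |
| 50 / 80 | 50:50 | 4.0% | 5.0% | 73.5% | 76.8% |
| 40 / 80 | 50:50 | 3.3% | 5.0% | 67.8% | 75.1% |
| 60 / 80 | 70:30 | 4.5% | 4.9% | 78.8% | 79.7% |
| 20 / 40 | 70:30 | 4.7% | 5.1% | 62.6% | 63.7% |

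**Simulation, set B.** 20,000 trials per scenario, 55:45 split, equal regions, log odds ratio −0.6 (odds ratio 0.549).

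| Slow / fast rate | Variance explained by strata | Size: formula | Size: chi-square | Size: CMH | Power: chi-square | Power: CMH |
|---|---|---|---|---|---|---|
| 50 / 75 | 6.5% | 4.3% | 4.5% | about 5% | 78.0% | 79.7% |
| 20 / 45 | 7.2% | 4.2% | 4.3% | 5.1% | 66.7% | 68.7% |
| 40 / 75 | 12.3% | 3.6% | 3.8% | 5.1% | 72.1% | 77.8% |

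**Reading the two sets together.** The power loss is nil with no slow-fast difference, 0.2 points at 10, about 1 to 1.6 at 20, 1.7 to 2.0 at 25, 3.3 at 30, 5.7 at 35 and 7.3 at 40. Where the stratum does not matter, CMH costs nothing beyond simulation noise.

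**The case against.** The strongest reply is that nothing important rests on this test. King's stage is listed among the other secondary endpoints (SAP 3.3.3), outside the family-wise control in SAP 7.3, and no sample size depends on it. The chi-square errs only on the safe side. The section also plans a time-to-event test and a comparison controlling for baseline stage. All of this stands and sets the severity. The baseline-stage comparison is only a partial answer, because baseline stage is not a randomisation factor.

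The link between decline rate and stage change may also be weak. Under SAP 8.4.2.8 the stage moves only when a new body region becomes involved, or on gastrostomy, ventilation need or death. Further loss within an affected region lowers the ALSFRS-R without changing the stage. Entry requires a decline of 1 to 4 points, so the strata divide a narrow range. This stands as well, and it is why the consequence has to be stated conditionally.

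Two stronger readings are tempting, and the documents do not support them:

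- A reader might infer that the test is certainly conservative, with a definite loss such as 2 to 6 points. That range appears only if one assumes slow-fast differences of 25 to 35 percentage points. The documents give no rates by stratum, and the range properly starts at zero.
- A reader might infer that the two tests of the same event adjust for different factors. Only stratified versus unstratified is established. SAP 9.2.1.4.4 and 9.2.1.4.5 refer back to a stratified log-rank test in 9.2.1.4.3. The visible text there describes a log-rank test without naming strata, and its code is redacted. That the strata are the randomisation factors is an inference.

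Nor do the simulations show a gain from stratifying by region, since the event rates varied only by decline rate. Including region rests on matching the analysis to the randomisation.

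**Conclusion.** The point holds in conditional form and is minor. The chi-square for both King's progression events ignores the randomisation strata. It remains a valid test. If decline rate predicts stage progression, its size falls below 5% and it gives up power: about 0 to 3 points for slow-fast differences of 10 to 30 percentage points, and 6 to 7 points only at 35 to 40. If decline rate is not prognostic, nothing is lost.

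These figures rest on assumed stratum rates, 380 subjects analysed, an odds ratio of about 0.55 and no region effect. The absence of named log-rank strata in 9.2.1.5.7 is a specification gap that needs no assumption about rates.

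A separate matter lies outside this point. SAP 8.4.2.8 carries the last stage forward when an assessment is missing, so an early dropout can be counted as a non-progressor. Stratifying would not change that.

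**What to change.** In SAP 9.2.1.5.7:

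- Replace the chi-square with a CMH test stratified by decline-rate stratum and region, for both events.
- Report the stratum-adjusted risk difference with its 95% CI.
- Name the same strata for the log-rank test.
- For the comparison of proportions controlling for baseline stage, specify a logistic model with treatment, decline-rate stratum, region and baseline stage. Adding stage to the CMH strata would be sparse: six possible stage categories (0, 1, 2, 3, 4A, 4B) × 6 strata give up to 36 cells, or 380/36 ≈ 11 subjects per cell if all were filled. Cells with one arm only, or with no variation in outcome, contribute nothing.

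The cost is a few words in one SAP section and a changed procedure option. No new data are needed, and neither the sample size nor the testing hierarchy changes. The only practical provision is a rule for pooling regions if a stratum turns out very small.

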6.1.2. Efficacy Full Analysis Set (FAS)

The FAS is defined as all randomized subjects who received at least 1 dose of study medication. Subjects in the FAS will be grouped and analyzed based on the planned treatment allocated (as randomized). Efficacy endpoints will be analyzed using the FAS.

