Since the MT-1186-A02 clinical trials will not collect information on King's Stage directly, ALSFRS-R item responses and patients' survival will be mapped to stages for every ALSFRS collected visit using the above published algorithm and patient-level data. Patients with baseline ALSFRS-R assessments that will not meet criteria for lower limb, upper limb, or bulbar involvement, and that also will not have evidence of Stage 4A or Stage 4B, will be designated "Stage 0", as their assessments could not be mapped to the King's ALS Clinical Staging System. For the King's stage derivation, the available ALSFRS-R data at each analysis visit will be used in the subjects who was not dead. If the subject was reported as a death from the last observation visit to last day of the nearest analysis visit window, King's stage from the analysis visit is Stage 5. If patients who was not death will have missing ALSFRS-R assessment at each visit, the last observation will be carried forward for the last King's stage value; In the vast majority of circumstances patients will either remain in the same clinical stage from one assessment to the next or they will experience a decline in stage. In those relatively rare instances, in which patients will be found to improve from one assessment to the next, the value from their immediately prior assessment will be used rather than the actual observed value, because the improvement will be considered to be temporary or spurious.

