8.5. Analysis Visit Definitions

The acceptable visit dates windows of observation, examination, and investigation are specified as in Table 5. Data obtained within the acceptable windows will be used for analysis or presentation. If the dates of observation, examination, or investigation are out of the following acceptable range, data obtained on those days will not be used for analysis or summary statistics. However, all data as captured will be listed.

The date of the first dose of study drug is defined as Day 1. Unless otherwise specified, baseline will be the last observed value of the parameter of interest prior to the first intake of study drug (this includes unscheduled visits). For other visits, if there are multiple data in a window, the closest data to nominal day will be used. If the distance to the nominal day is the same, the data of later date will be used.

Statistical Analysis Plan
Protocol No. MT-1186-A02

Mitsubishi Tanabe Pharma America, Inc.

Table 5 : The analysis visit windows

Analysis visit	Nominal day	Window	
		Except for laboratory test in Japan site	Laboratory test in Japan site
Baseline	Day 1	\leq Day 1	
Day 8	Day 8	-	Day 2 to 18
Week 4	Day 29	Day 2 to 42	Day 19 to 42
Week 8	Day 57	Day 43 to 71	
Week 12	Day 85	Day 72 to 127	
Week 24	Day 169	Day 128 to 211	
Week 36	Day 253	Day 212 to 294	
Week 48	Day 337	Day 295 to 379	

In case assessments are done at the Early Termination visit, these assessments will be used as data for the scheduled visit closest to the early termination time point, in case the corresponding data are missing from this visit.

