9.2.1.5. Other Secondary Efficacy Analyses

All available data regardless of use of additional/new AMX0035 treatment (ICE1) drug and all available data up to early discontinuation (ICE2) will be included. For analysis of King's ALS Clinical Stage, if death after early discontinuation (ICE2) was occurred, the death event will be included.

9.2.1.5.1. Changes from baseline in ALSFRS-R score at Weeks 4, 8, 12, 24, 36 and 48

The Change from baseline in ALSFRS-R score at Weeks 4, 8, 12, 24, 36 and 48 will be analyzed using the similar model as specified for the 1st key secondary analysis replacing the %SVC at baseline covariate with ALSFRS-R at baseline. The LSMEANS estimates for the mean change from baseline to Weeks 4, 8, 12, 24 and 36 and 48, as well as the difference of the estimates between oral edaravone 105 mg daily versus oral edaravone 105 mg on/off regimen will be displayed with their corresponding standard errors, p-values, and 95% CI. This endpoint will be analyzed using the FAS. The same analysis will be performed for ALSFRS-R subdomains.

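### The Week 48 King's-stage chi-square counts subjects who drop out before declining as progression-free, so progression is understated and unequal dropout can create a false difference (minor, other secondary endpoint)

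*SAP*

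**What the plan says.** - **Test.** SAP 9.2.1.5.7 defines two progression events: any decline in stage from baseline, and a decline of at least two stages. The proportions with each event by Week 48 are compared "using chi square test for proportions". The time to each event is compared by a stratified log-rank test with a Kaplan-Meier figure.
- **Dropouts in the time-to-event analysis.** "For the latter, study dropouts prior to any event will be treated as censored as of the date of their first missing assessment". The opening words confine this rule to the log-rank analysis.
- **Missing stages.** For a subject who has not died, SAP 8.4.2.8 says "the last observation will be carried forward for the last King's stage value". It also replaces any observed improvement by the preceding stage.
- **Data after discontinuation.** SAP 9.2.1.5 says "all available data up to early discontinuation (ICE2) will be included", with one exception for King's stage: "if death after early discontinuation (ICE2) was occurred, the death event will be included".
- **Denominator.** "The FAS is defined as all randomized subjects who received at least 1 dose of study medication" (SAP 6.1.2). No post-baseline efficacy data are required.
- **Early-termination visit.** Where the scheduled visit is missing, "these assessments will be used as data for the scheduled visit closest to the early termination time point" (SAP 8.5).
- **Level and tier.** "all statistical tests will be done as 2-sided at the 5% significance level" (SAP 7.2). King's stage is listed among the other secondary endpoints (SAP 3.3.3) and is not among the six hypotheses of the fixed sequence (SAP 7.3).

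**The concern.** Read together, these rules leave no gap for the proportions. A subject who stops at Week 12 without a decline, and is not known to have died, stays in the denominator with the Week 12 stage carried to Week 48. A dosed subject with no later ALSFRS-R keeps the baseline stage. In a disease where the SAP itself expects patients to hold their stage or worsen, carrying a stage forward can only miss later events.

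Two things follow. The reported progression percentages are too low. And if the arms lose different numbers of subjects for reasons unrelated to progression, the arm with more losses has less observed progression with no treatment effect behind it. The chi-square and the log-rank would then give two p-values for the same event under conflicting dropout rules, and the SAP does not say which leads.

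**Working it through.** **1. Inputs from the documents.** 190 per arm, 1:1; 30% dropout to Week 48 overall; two-sided 5% level; ALSFRS-R at Weeks 4, 8, 12, 24, 36 and 48.

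**2. The plan's own figure.** The documents give no rate or power for King's stage, so the only figure to reproduce is the one that supplies the sample size and dropout. Evaluable per arm: 190 × 0.70 = 133. Noncentrality: (2.6/7) × √(133/2) = 3.03. The noncentral t with 264 df gives 85.5% power, as stated.

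**3. Assumptions not in the documents.** True Week 48 progression *p* is equal in both arms and lies between 30% and 80%. Dropout *d* by arm is 30/30, 25/35 or 20/40 percent. Progression and dropout are independent and exponential. Deaths are not modelled separately.

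**4. Observed proportion under carry-forward.** Let F(w) = 1 − (1−p)^(w/48) and S(w) = (1−d)^(w/48). A subject whose last attended visit is w is an event only if the decline occurred by w:

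observed = Σ F(wᵢ) × [S(wᵢ) − S(wᵢ₊₁)], with the last term F(48) × S(48).

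For p = 0.80, d = 0.30:

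| w | F(w) | share last seen at w | product |
|---|---|---|---|
| 4 | 0.126 | 0.028 | 0.004 |
| 8 | 0.235 | 0.028 | 0.006 |
| 12 | 0.331 | 0.078 | 0.026 |
| 24 | 0.553 | 0.071 | 0.039 |
| 36 | 0.701 | 0.065 | 0.046 |
| 48 | 0.800 | 0.700 | 0.560 |

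Sum: 0.681. True 60% appears as 50.1%, and true 30% as 24.6%.

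If every dropout has an assessment at the moment of leaving, then with λp = −ln(1−p)/48 and λd = −ln(1−d)/48, observed = λp/(λp+λd) × [1 − (1−p)(1−d)]. For the same case this is 0.819 × (1 − 0.2 × 0.7) = 0.704.

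**5. Type I error of the chi-square.** With observed proportions o₁ and o₂, difference D and mean ō: se₀ = √(2ō(1−ō)/190) and se₁ = √([o₁(1−o₁)+o₂(1−o₂)]/190). The rejection rate is Φ((D − 1.96 se₀)/se₁) plus the opposite tail.

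Example, p = 0.80 and dropout 20% vs 40%: o₁ = 0.722, o₂ = 0.638, D = 0.085 before rounding, se₀ = 0.0479, se₁ = 0.0477. Then Φ((0.085 − 0.0938)/0.0477) = 42.6%.

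| True progression | 30/30 | 25/35 | 20/40 | 20/40, full early-termination data |
|---|---|---|---|---|
| 30% | 5.0% | 7.1% | 13.7% | 11.1% |
| 60% | 5.0% | 10.5% | 27.8% | 20.9% |
| 80% | 5.0% | 14.3% | 42.6% | 31.8% |

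At a 50% rate with 20/40 dropout the figure is 22%, so the 43% belongs to the 80% rate only. A milder split of 28/32 at 80% gives about 6.4% (6.0% with full early-termination data).

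**6. Check by simulation, and the alternative.** In 4,000 simulated trials per scenario (unequal dropout, p = 30–80%, log-rank unstratified), false-positive rates were:

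| Analysis | Range |
|---|---|
| Chi-square with carry-forward | 7.6–43.7% |
| Log-rank, censored at first missing assessment (the SAP rule) | 5.5–7.6% |
| Log-rank, censored at last attended visit | 4.9–5.5% |

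The SAP's censoring date is later than the last time the subject was seen event-free, which leaves a small excess.

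**The case against.** The strongest reply is that the sound analysis is already planned: the same sentence pairs the chi-square with a log-rank test that censors dropouts, and a Kaplan-Meier figure follows. The endpoint carries no confirmatory claim. This stands, and it limits the severity. It does not remove the biased p-value and percentages, which would still be reported.

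Three stronger readings are tempting, and the documents do not support them.

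- **That every dropout is scored as a non-progressor.** They keep the last observed stage. At 60% true progression and 30% dropout, (0.501 − 0.70 × 0.60)/0.30 = 27% of dropouts had already declined and count as events. Deaths after discontinuation also count. Early-termination assessments are used (SAP 8.5), and Protocol 9.6 and 10.1.4 ask sites to make every effort to obtain them.
- **That the arm losing more subjects must look better.** This needs losses unrelated to progression. Losses that are deaths, or progression recorded at the early-termination visit, enter as events. At equal dropout the test holds its 5% level.
- **That a large imbalance is expected.** Only 30% overall is stated. The arms are blinded, and edaravone and placebo are identical in appearance (Protocol 14.5). The 20/40 split is a stress case, not a forecast.

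**Conclusion.** The concern holds, at minor severity. As written, the Week 48 chi-square understates King's-stage progression whenever subjects drop out before declining, and it can produce a false difference when non-informative dropout differs between arms. In the illustration, true 80% progression is shown as 68–70%. Type I error runs from 5% at equal dropout to about 14% at 25% vs 35%, and up to about 43% at 20% vs 40%, the highest value being at an 80% progression rate.

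These sizes rest on assumed progression rates, assumed per-arm dropout and independent dropout. Early-termination data and counted deaths shrink the bias. Withdrawal because the disease has worsened (Protocol 9.6) could enlarge it where the decline is not recorded.

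A reader might infer that the trial's main result is at risk. It is not: King's stage lies outside the fixed sequence, and the primary CAFS analysis handles missing scores by multiple imputation (SAP 9.2.1.1).

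**What to change.** In SAP 9.2.1.5.7:

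1. Replace the chi-square comparison with Kaplan-Meier cumulative proportions at Week 48 by arm, their difference and a 95% CI, for both progression events, taken from the time-to-event analysis already planned.
2. Censor event-free dropouts at their last attended ALSFRS-R assessment rather than at the first missing one.
3. State how a death after discontinuation enters. SAP 9.2.1.5 counts it, while 9.2.1.5.7 censors the dropout, possibly before the death.
4. Report dropout by arm beside the result.
5. Keep carried-forward stages for the descriptive shift table only.

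The cost is SAP wording and one read-off from a planned fit; no new data are needed. Kaplan-Meier still assumes non-informative censoring, which withdrawal for worsening disease may violate, so the write-up should say so.
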